### Analytical Plan

Power analysis: Based on a preliminary data, the mean change of NF-kB DNA binding from baseline among patients who underwent six weeks XRT was 8.2 ng NF-kB per assay well (SD = 9.0). We hypothesize that in this study the patients in the placebo group will have the similar response as in the preliminary data, and patients who receive Meriva, the mean change of NF-kB DNA-binding level from baseline to 6 weeks post XRT is 0.0 with a reduced SD of 4.5. Based on alpha of 0.05 and a n = 11 per group, we will have 82% power to detect the above hypothesized difference by one-sided two-sample t test. We believe such a difference is clinically meaningful and is well within the range of differences observed in chemotherapy vs. no chemotherapy patients and fatigued vs. non-fatigued patients.

Statistical analysis plan: Primary objectives: the mean changes of NF-kB DNA binding from baseline to Week 6 will be compared between two groups using two-sample t test. The change of plasma concentration of NF-kB downstream mediators from baseline will be compared between two groups using two-sample t-test/Wilcox sum rank test for continuous measures and using Chi-square test/Fisher's exact test for categorical measures. Secondary objectives: The change of MFI over time in two groups will be compared by the GEE model.

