The change to 2g/d dose is supported by Mantovani and colleagues who reported beneficial effects of 2g/d Meriva on inflammatory biomarkers in cancer patients taking Meriva for 1 month (50). Also supporting this modification is a trial comparing the analgesic effects of 1.5g vs. 2g Meriva in a mixed patient group with different sources of pain (e.g. arthritis, neuropathy, recurrent headaches) (51). In general the results of this study suggest that Meriva at 2g/d may be more efficacious than Meriva at 1 g/d. Finally, a recent paper by Drobic and colleagues found that 2g/d decreased inflammatory markers and muscular damage in healthy men undergoing intense physical exercise (52). No tolerability issues were noted in either of these studies except for mild nausea and heartburn in the report by Di Pierro et al. (51), which was attributed to the bulk of capsules consumed and not the content of the capsules.

Of note, because of difficulty obtaining enough cells from the blood of the first 10 subjects who completed the study, we were unable to measure peripheral blood NF-kB DNA binding. Therefore, because we could not statistically compare NF-kB DNA binding between groups, the Meriva dose of 1 g per day was maintained without an increase (as per protocol). In addition, statistical consultation based on IL-6 values in the first 10 completed subjects suggested that continuing enrollment at the Meriva 1 mg dose would give sufficient power (>0.80) to detect a difference in this NF-kB-related inflammatory endpoint at study completion or after enrollment of at least 40 subjects. Similar findings were observed with fatigue. For these reasons, the Meriva dose will be continued at 1mg per day for the entirety of the study for all subjects.

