#### (vi) Observations and measurements

Based on work performed in prior studies, we do not anticipate biomarker responses that would suggest adverse reactions to Meriva (1-4). We will therefore not collect blood samples during the 6 week treatment with Meriva to monitor adverse biomarker responses. Research blood will be collected at baseline during the last week of XRT or up to three months post XRT and at the conclusion of the 6 weeks treatment with Meriva. Patients will be interviewed weekly by phone to ensure they are not experiencing side effects previously described for curcumin, including nausea and diarrhea. If they do report worsening of these symptoms compared to before they started Meriva, they will be asked to immediately discontinue taking Meriva and come to the clinic for full physical evaluation. In the case that a patient experiences adverse side effects and stops taking Meriva, self-report information and blood samples will still be collected at the early termination visit.

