#### Curcumin Visit II: Baseline (XRT end – last week of XRT or within 3 months after)

- Inclusion criteria completed

[figure not shown]
- Mediterranean diet survey, Inventory of Depressive Symptomatology – Self Reported (IDS-SR)[41], Pittsburgh Sleep Quality Index (PSQI) [42-45], Perceived Stress Scale (PSS)[46], Godin Leisure-Time Exercise Questionnaire (GLTEQ)[48], Multidimensional Fatigue Index (MFI) (36) and PROMIS Fatigue Short form [49]
- Self-report of fatigue level and pain on a scale of 0-10, 0 being none and 10 being extreme.
- Fasting blood draw for research (two 4 ml purple tops, two 6 ml purple tops, and 1 tempus tube)
- Ultrasound scan and photographs at PI's discretion
- Randomization
- Dispense medications and medication diary
- Patient reimbursement

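### Baseline is subtracted but never used as a covariate; a pre-specified ANCOVA for the plasma mediators and MFI is a cheap and probable, but not guaranteed, gain in precision

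*Combined protocol and SAP*

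**What the plan says.** All of the planned comparisons are in the Analytical Plan.

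- NF-kB DNA binding: "the mean changes of NF-kB DNA binding from baseline to Week 6 will be compared between two groups using two-sample t test".
- Continuous mediators: "The change of plasma concentration of NF-kB downstream mediators from baseline will be compared between two groups using two-sample t-test/Wilcox sum rank test".
- MFI: "The change of MFI over time in two groups will be compared by the GEE model". The model terms are not listed.

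No analysis names a baseline covariate, although baseline values will exist. Section (vi), Observations and measurements, states: "Research blood will be collected at baseline during the last week of XRT or up to three months post XRT". The Visit II list includes "Multidimensional Fatigue Index (MFI) (36) and PROMIS Fatigue Short form [49", and the study checklist places MFI only at Visit II and at Visit III or early termination.

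The power analysis covers NF-kB DNA binding only. It assumes a placebo change of 8.2 (SD 9.0) and a Meriva change that "is 0.0 with a reduced SD of 4.5". Section (v), Dosing, reports that NF-kB binding could not be measured in the first 10 completers. It then cites power above 0.80 for IL-6 "at study completion or after enrollment of at least 40 subjects", and adds: "Similar findings were observed with fatigue".

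**The concern.** Subtracting baseline fixes its coefficient at 1. ANCOVA estimates that coefficient from the data. When the true slope is not 1, the change score carries avoidable noise.

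With 60 patients planned, this matters most for the mediators and MFI. Section (v) relies on power for IL-6 and fatigue without showing the inputs. No power is stated for TNF-alpha, sTNFR2, IL-1ra or CRP. Baseline adjustment is a way to sharpen these comparisons without more patients, visits or assays.

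The open GEE wording does not clearly supply the adjustment. With two visits, a model with group, time and their interaction has four parameters for four cell means. With complete data its interaction is therefore exactly the between-arm difference in mean change.

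**Working it through.** **Inputs from the documents.** Changes 8.2 (SD 9.0) and 0.0 (SD 4.5); n = 11 per group; one-sided alpha 0.05; stated power 82% (Analytical Plan). Planned enrolment is 30 per arm (sections (iii) and (iv)).

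**Assumptions.** Rho is 0.3, 0.5, 0.7 or 0.9. The ratio k = Week-6 SD / baseline SD is 0.8 to 1.5. Tests after step 1 are two-sided at 0.05, because the analysis plan states no sidedness.

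**1. The plan's own figure.** SE = sqrt(81/11 + 20.25/11) = 3.034. Noncentrality = 8.2/3.034 = 2.703. Welch df = 14.7. One-sided power is 82.4% (83.3% with the pooled test), so the stated 82% reproduces.

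**2. Variance ratio.** With baseline SD s:

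- Var(change) = s²(1 + k² − 2·rho·k)
- ANCOVA residual variance = s²k²(1 − rho²)
- f = k²(1 − rho²)/(1 + k² − 2·rho·k), so 1 − f = (1 − rho·k)²/(1 + k² − 2·rho·k)

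Thus f cannot exceed 1, and it equals 1 when rho·k = 1. ANCOVA then gains nothing and still pays its degree of freedom.

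**3. An endpoint with 80% change-score power.** At 30 per arm the noncentrality is 2.849. Under ANCOVA it becomes 2.849/sqrt(f) with 57 df. Example: k = 1, rho = 0.5 gives f = 0.75, noncentrality 3.290 and power 89.9%.

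| k | rho 0.3 | 0.5 | 0.7 | 0.9 |
|---|---|---|---|---|
| 0.8 | 97.7% | 95.9% | 94.2% | 94.9% |
| 1.0 | 93.5% | 89.9% | 85.9% | 82.0% |
| 1.25 | 88.5% | 84.2% | 80.7% | 82.0% |
| 1.5 | 85.1% | 81.4% | 80.1% | 88.8% |

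Results at 20 per arm agree within 0.1 point.

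Simulation (20,000 runs per cell) comes out slightly lower, because chance baseline imbalance also costs something. With k = 1 and ordinary errors it gives 93.2/89.3/85.4/80.8% at 30 per arm. The worst cell is k = 1.5, rho = 0.7:

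- 20 per arm: 78.5% with ordinary errors, 76.1% with HC3 robust errors
- 30 per arm: 79.2% and 77.6%

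**4. An endpoint that reaches 80% at 20 per arm, run at 30.** This is one reading of the IL-6 statement. Noncentrality = 2.875 × sqrt(1.5) = 3.521, and the t test has 93.3%. ANCOVA with k = 1 gives 99.0/97.9/96.4/94.4% by formula. Simulated values are 97.0/95.0/93.4/94.3% at k = 1.25 and 95.9/93.9/93.2/97.2% at k = 1.5. The gain is about 0 to 6 points.

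**5. NF-kB DNA binding at the planned effect.** Suppose the ten patients without a value split evenly, leaving 25 per arm. SE = sqrt(101.25/25) = 2.012, noncentrality 4.07, power 97.7%. At 30 per arm: SE 1.837, noncentrality 4.46, power 99.2%. Simulated HC3 ANCOVA at 25 per arm gives 99.8/99.3/98.7/97.8%, a gain of about 2 points or less.

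The interval depends on how SDs of 9.0 and 4.5 arise. Under one favourable structure the 95% half-width at 25 per arm goes from 4.06 to 3.48/3.70/3.90/4.10 ng per well. But randomisation gives both arms the same expected baseline SD. With rho = 0.5 in both arms and k = 1 under Meriva, s² = 20.25. Placebo then needs 81 = 20.25(1 + k² − k), so k = 2.30. Across structures of this kind (same rho in both arms, 0.3 to 0.7), simulated half-widths were 3.96 to 4.23. That runs from 2% narrower (3.96/4.06 = 0.975) to 4% wider (4.23/4.06 = 1.042).

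**6. GEE check.** In 20 simulated complete two-visit datasets, under independence and exchangeable working correlations, the group-by-time coefficient equalled the change-score difference to 1e-15.

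**The case against.** The strongest reply is that nothing here is an error. A change-score comparison in a randomised trial is unbiased, and it does use the baseline by subtracting it. That stands. A reader might infer that the planned tests are biased, or that the baseline data are discarded. The documents support neither reading.

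Second, for NF-kB DNA binding, which section (v) calls the primary study endpoint, power is near its ceiling and the interval might even widen. That also stands, so the case cannot rest on NF-kB.

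Third, the gain rests on an unstated rho and k. At k = 1.25 to 1.5 and rho near 0.7 it vanishes or turns into a small loss. Requiring a fatigue score over 3 at entry may compress baseline MFI and push k above 1, so MFI could fall in that region. This limits the promise, but the likely cost is small.

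Fourth, the plan already allows a rank-sum test for the mediators. The gains above are against a t test only, and no skewed data were simulated. This is a reason to keep the rank-sum test as a named sensitivity analysis.

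Fifth, the GEE terms are not given, so a baseline covariate is not excluded. That is true, and stating the terms would settle it.

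**Conclusion.** The point holds as an optional improvement in efficiency, not as a defect in validity. For the continuous mediators and MFI, baseline adjustment probably improves precision. Where change-score power is about 80%, the formula gain is roughly 2 to 14 points with equal visit SDs, about 0 to 9 with k = 1.25-1.5, and about 14 to 18 with k = 0.8. An endpoint already at 93% gains about 0 to 6 points when k is 1 or more.

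It would be tempting to quote one figure from this range as the expected gain, or to promise a narrower NF-kB interval. The documents give no correlation and no visit-specific SDs, so they support neither. Nor do the figures show that the NF-kB comparison is underpowered at its planned effect.

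Confidence is medium: the algebra is firm, but the size rests on assumed rho and k.

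**What to change.** Before unblinding, specify in the Analytical Plan:

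- **Mediators (continuous) and MFI:** the main analysis is an ANCOVA of the Week-6 value on treatment and the outcome's own baseline. For MFI, a GEE of the post-baseline value with baseline as a covariate serves equally. State the model terms.
- **Sensitivity analyses:** keep the change-score t test and the rank-sum test, named as such.
- **NF-kB DNA binding:** the same model may be used, with robust (HC3) errors because the plan expects unequal SDs. Claim little gain for it.
- **Standard errors elsewhere:** ordinary errors, unless variances clearly differ between arms.

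The cost is SAP wording, a regression in place of a t test, and one degree of freedom per outcome. No new data are needed. Power may fall by about 1 to 2 points with ordinary errors (k about 1.25-1.5, rho about 0.7), or by up to about 4 points with HC3 at 20 per arm.

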
Patients with anemia (HEM < 10g/dl) at baseline will be excluded unless otherwise approved by the PI or PI's designee. In addition, patients who develop evidence of infection (as determined by history, physical exam or laboratory testing) during the study will be discontinued from the study unless otherwise approved by the PI or PI's designee. Patients will be asked to refrain from having more than one alcoholic beverage per day.

This protocol proposes to enroll 60 total patients, with 30 randomized to the Meriva arm and 30 randomized to the placebo arm of the study.

[figure not shown]

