### Outcome Measures

The primary outcome to be measured will be the change in NF-kB DNA binding and its downstream mediators (plasma concentrations of TNF-alpha, sTNFR2, IL-1ra, IL-6 and CRP) after six weeks of treatment with daily placebo or Meriva. The secondary endpoint will be the change in fatigue from baseline to six weeks after treatment with Meriva or placebo. . Microarray analysis will also be performed before and after treatment to look at the expression of NF-kB response genes: **Primary Hypothesis: Patients responsive to Meriva will have decreased NF-kB DNA binding, decreased activation of NF-kB responsive genes and decreased downstream mediators of NF-kB pathway activation.**

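### MFI fatigue is to be compared by a GEE with no small-sample correction, working correlation or missing-data rule, on at most 30 patients per arm and two visits

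*Combined protocol and SAP*

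**What the plan says.** The statistical analysis plan (section Analytical Plan) gives fatigue one sentence: "The change of MFI over time in two groups will be compared by the GEE model". Working correlation, variance estimator, reference distribution, baseline adjustment and missing-data handling are not mentioned.

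Outcome Measures defines the endpoint: "The secondary endpoint will be the change in fatigue from baseline to six weeks after treatment with Meriva or placebo". Section (i) lists MFI fatigue among the secondary objectives; NF-kB DNA binding and its downstream mediators are primary.

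Section (iii) sets the size: "60 total patients, with 30 randomized to the Meriva arm and 30 randomized to the placebo arm". Section (v), in a remark on power for IL-6 that it then extends to fatigue, speaks of sufficient power "at study completion or after enrollment of at least 40 subjects".

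MFI is scheduled at Visit II (baseline) and Visit III (final evaluation). The study checklist also marks it at early termination, and section (vi) says self-report data are still collected from patients who stop because of side effects.

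**The concern.** Two features of an ordinary GEE matter at this size.

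First, its usual sandwich standard error with a normal reference is a large-sample device. With a few dozen patients it understates uncertainty, so a chance difference in fatigue is declared significant more often than the nominal rate.

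Second, under working independence a GEE sets the baseline scores of everyone against the Week 6 scores of those who stayed. If the patients lost differ at baseline, and differ in a way that is not the same in the two arms, the comparison shifts. The protocol has routes to loss after randomisation: discretionary exclusion below 75% of medication, discontinuation for infection, and stopping for gastrointestinal symptoms.

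Fatigue is the one patient benefit named in section (xi), so the interval reported for it should have its stated coverage.

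**Working it through.** **The plan's own figures.** None can be reproduced for MFI. The fatigue power remark in section (v) gives no inputs. The stated 82% power is for NF-kB binding. It does reproduce (difference 8.2, SDs 9.0 and 4.5, 11 per group, one-sided 0.05: 82.4% with Welch df 14.7, 83.3% with pooled df 20), but it has no bearing on the MFI analysis.

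**Inputs.** From the documents: two visits and n = 30 per arm, with n = 20 if 40 patients are split evenly. Assumed: a two-sided 5% test, group-by-visit terms, uncorrected sandwich variance and a normal reference.

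**Step 1: interval width, complete data.** With two visits and group, visit and group-by-visit terms, the GEE estimate equals the difference in mean change, whatever the working correlation. The uncorrected sandwich variance is (n − 1)/n times the unbiased one. Hence

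- type I error = 2·P(t with 2n − 2 df > 1.96·√((n − 1)/n))
- width ratio = 1.96·√((n − 1)/n) / t(0.975, 2n − 2)

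| n per arm | Type I error | Width ratio | Too narrow by |
|---|---|---|---|
| 30 | 5.9% | 0.963 | 3.7% |
| 25 | 6.1% | 0.955 | 4.5% |
| 20 | 6.4% | 0.944 | 5.6% |

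At 30 per arm, using z instead of t with an unbiased standard error would by itself give 5.5%; the variance factor adds the rest.

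**Step 2: bias from loss.** The documents give no dropout rate or visit correlation, so everything here is assumed. I simulated 4,000 trials per setting, 30 per arm, with no treatment effect and scores of SD 1 at both visits. Higher scores mean more fatigue. Loss of the Week 6 score follows a logistic function of baseline, with slope 0, 1 or −1. Entries are bias in SD units, with 95% coverage in brackets. Simulation error is about 0.004 SD for bias (√(2/30)/√4000) and 0.3 points for coverage (√(0.95·0.05/4000)).

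| Dependence on baseline | Loss by arm | Correlation | GEE, independence | GEE, exchangeable | ANCOVA, t reference |
|---|---|---|---|---|---|
| No loss | 0 / 0 | 0.5 | −0.005 (94.1%) | −0.005 (94.1%) | −0.004 (94.7%) |
| Same in both arms | 22% / 22% | 0.5 | −0.006 (94.1%) | −0.006 (94.1%) | −0.006 (95.2%) |
| One arm only | 18% / 22% | 0.5 | −0.093 (92.8%) | 0.001 (93.6%) | 0.001 (95.3%) |
| One arm only | 18% / 22% | 0.7 | −0.135 (90.8%) | −0.003 (93.9%) | 0.000 (95.4%) |
| One arm only, unequal loss | 10% / 30% | 0.5 | −0.125 (92.6%) | 0.005 (93.9%) | 0.002 (95.2%) |
| Opposite in the two arms | 22% / 22% | 0.5 | −0.192 (89.4%) | −0.010 (93.5%) | −0.005 (94.7%) |

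The independence bias is the correlation times the shift in completers' baseline mean. In the third row the implied shift is −0.093/0.5 ≈ −0.19 SD. Reversing the slope, so that the less fatigued leave, turns −0.09 into +0.09.

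Exchangeable correlation removes the bias but not the short intervals: its coverage stays at 93.5% to 94.1%.

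**Step 3: which GEE correction fits.** In the complete-data model of step 1 each patient's leverage is 1/n. Kauermann-Carroll multiplies the sandwich variance by n/(n − 1), which restores the unbiased value; with t on 2n − 2 df the width is correct. Mancl-DeRouen multiplies by (n/(n − 1))². At 30 per arm the interval is then √(30/29) = 1.017 times the correct width, and type I error is 4.6%.

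**The case against.** The plan says only that a GEE will be used. The uncorrected variance, the normal reference and working independence are readings of that sentence, and an analyst could run it with a correction and an exchangeable correlation. That stands: the defect is that the plan leaves these choices open. A reader might infer that the stated method is shown to exceed 5%, but the documents do not fix the estimator, so the figure is conditional on the usual default.

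A reader might also infer that dropout related to baseline fatigue is enough to bias the result. It is not. Equal dependence in both arms cancels, and exchangeable correlation brings the bias to about zero. Baseline MFI precedes treatment and the trial is double-blind, so arm-specific dependence needs some mechanism, such as side effects, that the documents do not establish. Nor do they support the inference that such dropout would look like a Meriva benefit: the sign depends on which patients leave and from which arm.

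The early-termination visit also collects MFI, which reduces missing scores. That stands too, but it does not help with patients who do not return, and the plan does not say whether an early score is used as Week 6.

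Finally, the error-rate effect is under one percentage point at the planned size, and 20 per arm comes from a power remark, not from a revised enrolment target. Both are fair and limit the weight of the point.

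**Conclusion.** The point holds as an under-specified secondary analysis whose usual default is mildly anti-conservative. With an uncorrected sandwich variance and normal reference, type I error is 5.9% at 30 per arm and 6.4% at 20, and intervals are 3.7% and 5.6% too narrow. These figures follow from the design and do not depend on the working correlation when data are complete.

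The bias is a separate, conditional risk. It needs both working independence and baseline-dependent loss that differs by arm. It is then about 0.09 to 0.135 SD when only one arm is affected and 0.19 SD in the extreme case of opposite dependence, in either direction. The loss rates, slopes, correlations and equal SDs behind those figures are assumptions.

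Nothing here touches the primary NF-kB comparison. The change is worth making because it is cheap and settles an analyst's choice that could otherwise move the fatigue estimate.

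**What to change.** Replace the GEE sentence in the Analytical Plan with, for example:

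> MFI at baseline and Week 6 will be analysed in all randomised patients by a linear mixed model (REML, unstructured 2×2 covariance, common baseline mean, visit and group-by-visit terms) with Kenward-Roger degrees of freedom. The Week 6 difference between groups will be reported with a 95% confidence interval.

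ANCOVA of Week 6 MFI on baseline MFI with a t reference is equivalent in complete data, and is the version simulated above.

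State whether an early-termination MFI counts as Week 6.

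If GEE is kept, specify an exchangeable working correlation and a Kauermann-Carroll corrected variance with a t reference. Mancl-DeRouen is usable but slightly conservative here. A variance correction without the exchangeable correlation would leave the conditional bias in place.

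The cost is a few sentences, with no new data and standard software. The small-sample correction alone widens intervals by about 4% (1/0.963) at 30 per arm and 6% (1/0.944) at 20. Baseline adjustment would be expected to offset this: relative to change scores it multiplies the standard error by √((1 + ρ)/2), where ρ is the correlation between visits, which is 0.87 at ρ = 0.5 and 0.92 at ρ = 0.7, assuming equal SDs at the two visits.
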